#### 10.1.3 Definition of Unanticipated Problems (UP)

OHRP considers unanticipated problems involving risks to participants or others to include, in general, any incident, experience, or outcome that meets all of the following criteria:

- Unexpected in terms of nature, severity, or frequency given (a) the research procedures that are described in the protocol-related documents, such as the IRB-approved research protocol and informed consent document; and (b) the characteristics of the participant population being studied;
- Related or possibly related to participation in the research ("possibly related" means there is a reasonable possibility that the incident, experience, or outcome may have been caused by the procedures involved in the research); and

- Suggests that the research places participants or others at a greater risk of harm (including physical, psychological, economic, or social harm) than was previously known or recognized.

This study will use the OHRP definition of UP.

## 10.2 Classification of an Adverse Event

### 10.2.1 Severity of Event

All AEs will be assessed by the clinician using a protocol defined grading system. For AEs not included in the protocol defined grading system, the following guidelines will be used to describe severity.

**Mild** – Events require minimal or no treatment and do not interfere with the participant's daily activities.

**Moderate** – Events result in a low level of inconvenience or concern with the therapeutic measures. Moderate events may cause some interference with functioning.

**Severe** – Events interrupt a participant's usual daily activity and may require systemic drug therapy or other treatment. Severe events are usually potentially life-threatening or incapacitating.

### 10.2.2 Relationship to Study Agent

In a clinical trial, the study product must always be suspect. To help assess, the following guidelines are used.

For all collected AEs, the clinician who examines and evaluates the participant will determine the AE's causality based on temporal relationship and his/her clinical judgment. The degree of certainty about causality will be graded using the categories below.

- **Definitely Related** – There is clear evidence to suggest a causal relationship, and other possible contributing factors can be ruled out. The clinical event, including an abnormal laboratory test result, occurs in a plausible time relationship to drug administration and cannot be explained by concurrent disease or other drugs or chemicals. The response to withdrawal of the drug (de-challenge) should be clinically plausible. The event must be pharmacologically or phenomenologically definitive, with use of a satisfactory re-challenge procedure if necessary.
- **Probably Related** – There is evidence to suggest a causal relationship, and the influence of other factors is unlikely. The clinical event, including an abnormal laboratory test result, occurs within a reasonable time after administration of the drug, is unlikely to be attributed to concurrent disease or other drugs or chemicals, and follows a clinically reasonable response on withdrawal (de-challenge). Re-challenge information is not required to fulfill this definition.
- **Possibly Related** – There is some evidence to suggest a causal relationship (e.g., the event occurred within a reasonable time after administration of the trial medication). However, other factors may have contributed to the event (e.g., the participant's clinical condition, other concomitant events). Although an AE may rate only as "possibly related" soon after discovery, it can be flagged as requiring more information and later be upgraded to "probably related" or "definitely related," as appropriate.
- **Unlikely to be related** – A clinical event, including an abnormal laboratory test result, whose temporal relationship to drug administration makes a causal relationship improbable (e.g., the event did not occur within a reasonable time after administration of the trial medication) and in which other drugs or chemicals or underlying disease provides plausible explanations (e.g., the participant's clinical condition, other concomitant treatments).
- **Not Related** – The AE is completely independent of study drug administration, and/or evidence exists that the event is definitely related to another etiology. There must be an alternative, definitive etiology documented by the clinician.

### 10.2.3 Expectedness

Principle investigator will be responsible for determining whether an AE is expected or unexpected. An AE will be considered unexpected if the nature, severity, or frequency of the event is not consistent with the risk information previously described for the study agent.

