#### Long-range risks

- TA weakness resulting in foot drop
- Lateral compartment weakness resulting in eversion weakness
- Plantarflexion weakness resulting in weakness with plantarflexion
- Distant spread resulting in botulism-like symptoms including muscle weakness all over body, vision problems, difficulty speaking or swallowing, trouble breathing, loss of bladder control, respiratory compromise, death (see black box warning of Botox labelling)

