#### 4.1.3 Primary Safety Endpoints

1. Lower extremity weakness
2. Bruising, bleeding, pain, redness, or swelling where the injection was given

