### 9.3 Data Management

Investigator, [name], will serve as the DCC for the study. The DCC agrees to be responsible for implementing and maintaining quality control and quality assurance systems with written standard operation procedures (SOPs) to ensure that trial is conducted and data are generated, documented, and reported in compliance with the protocol, accepted standards of Good Clinical Practice (International Conference on Harmonization E6), and all applicable federal, state, provincial, and local laws, rules, and regulations relating to the conduct of the clinical trial in an ongoing and auditable manner.”

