#### **10.4.1 Adverse Event Reporting**

Any other AE/SAEs that meet the definition of an unanticipated problem as described above must be reported to the HS or MR IRB within 14 business days.

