#### **10.6 Safety Oversight**

The Principal Investigator will serve as the DMC. REDCap will provide the DMC and the study biostatistician the ability to efficiently collect the needed data and provide safety oversight of the protocol.

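### IRB reporting of a serious distant-spread event rests on the principal investigator's own expectedness call, and the symptoms of distant spread are not collected by name

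*Combined protocol and SAP*

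**What the plan says.** Section 2.7.1 (Long-range risks) names the risk: "Distant spread resulting in botulism-like symptoms including muscle weakness all over body, vision problems, difficulty speaking or swallowing, trouble breathing". The same bullet goes on to "loss of bladder control, respiratory compromise, death (see black box warning of Botox labelling". Section 2.3 also describes it, and 2.7.2 confirms its boxed-warning status.

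The primary safety endpoints in 4.1.3 are two: "Lower extremity weakness" and "Bruising, bleeding, pain, redness, or swelling where the injection was given". Section 10.1 repeats those two and adds nothing on distant spread.

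Section 10.2.3 makes the principal investigator responsible for grading expectedness, with this test: "An AE will be considered unexpected if the nature, severity, or frequency of the event is not consistent with the risk information previously described".

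On reporting, 10.4.1 reads "Any other AE/SAEs that meet the definition of an unanticipated problem as described above must be reported to the HS or MR IRB", with 14 business days allowed. Section 10.4.2 sends deaths and immediately life-threatening events to the DCC/study sponsor within 24 hours and other SAEs within 72 hours, whatever their relationship to treatment.

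On oversight, 10.6 says "The Principal Investigator will serve as the DMC", and 11.1 makes the same person the medical monitor. In 9.3 an investigator "will serve as the DCC for the study".

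**The concern.** Distant spread is the gravest harm that the protocol itself names, and the use under study is not an approved one (2.3). Whether the IRB hears of a serious case depends on a judgement by the person who runs the study and also acts as its DMC and medical monitor. The protocol gives that judgement little to rest on, since its text states no rate for distant spread and no rule for this event. Enrolment runs over 18 months (section 5), so further subjects could be injected before anyone shown to be independent of the investigators has looked at a case.

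The second issue is capture. Safety and tolerability is a stated objective (section 3), but no contact is set up to ask about vision, speech, swallowing, breathing, bladder control or general weakness by name. Mild cases may then go unrecorded.

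**Working it through.** The plan states no figure on this point, so the check traces each written route from an event to the IRB.

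| Section | What triggers it | Recipient | Clock |
|---|---|---|---|
| 10.4, Immediate Report | Unanticipated problem, at a site under the UW IRBs, and an immediate threat to other current subjects | IRB | 1 business day |
| 10.4.1 | Any other AE/SAE that is an unanticipated problem | IRB | 14 business days |
| 10.4.3 | Unanticipated problem that is an SAE | IRB and DCC/sponsor | 24 hours |
| 10.4.2 | Death or immediately life-threatening event | DCC/sponsor | 24 hours |
| 10.4.2 | Other SAE | DCC/sponsor | 72 hours |
| 10.4.2 | Unexpected fatal or life-threatening suspected reaction | FDA | 7 calendar days |
| 5.7.1 and 10.5 | Study suspended or terminated | IRB | Promptly |

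**Step 1: the filter.** All three event-based IRB routes require an unanticipated problem. Under 10.1.3 that means meeting all three criteria: unexpected, at least possibly related, and suggesting greater risk than previously known or recognized. The first and third depend on what has already been described. Distant spread up to death is described in both 2.3 and 2.7.1. A case could therefore be called unexpected on frequency and still be judged to fail the third criterion.

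**Step 2: what is left if the filter is not passed.** Two 10.4.2 routes to the DCC/sponsor remain. The FDA route is limited to unexpected events. The halting route reaches the IRB only if someone decides to suspend or terminate, and 10.5 sets no event that compels this.

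**Step 3: does the frequency limb settle the grade?** The protocol text offers only a qualitative statement (2.7.1, Rationale) that serious side effects are of minimal likelihood. Taking the true rate p as an assumption, the chance of at least one case among the 10 subjects is 1 − (1 − p)^10:

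- p = 0.1%: 1.0%
- p = 0.5%: 4.9%
- p = 1%: 9.6%
- p = 2%: 18.3%
- p = 5%: 40.1%

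The chance falls below 5% when p is below 1 − 0.95^(1/10) = 0.51%. If minimal means less than about 0.5%, a single case would be hard to reconcile with it, which points to unexpected. At 1% or more it would not. One case in 10 has an exact 95% interval of 0.25% to 44.5%, so the observed count cannot decide the matter. The grade stays with the principal investigator.

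**Step 4: the clocks.** A serious unanticipated problem that does not threaten other current subjects has 14 business days under 10.4.1 and 24 hours under 10.4.3. Where it does threaten them, 10.4 gives 1 business day and 10.4.3 gives 24 hours. These passages must be reconciled.

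**Step 5: capture.** Table 4 lists a side-effect evaluation at 2, 4 and 6 months without naming symptoms. Section 10.3 says only that the investigator asks about events since the last visit. Section 6.6 puts onset at about 2 weeks, so before the 2-month visit detection relies on the subject making contact.

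**The case against.** A reader might infer that a listed risk is automatically expected, so that a fatal case would never reach the IRB. The documents do not support that. The 10.2.3 test turns on nature, severity or frequency, and listing settles only the first and perhaps the second. The minimal-likelihood statement in 2.7.1 points towards unexpected. So does the list of expected side effects in 6.4, which names only weakness of the injected muscle and injection-site pain and bleeding. If the other criteria are met as well, the IRB is due a report within 24 hours under 10.4.3. This stands: a careful investigator may well report such a case. It remains true that nothing written requires that reading.

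Section 2.7.1 also points to a package insert in an appendix, and 10.4 to the IRB's own standard protocols. Neither was available here. The insert may give a rate and the IRB rules may ask for more, so the finding covers only the rules written in the protocol.

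A reader might also infer that no independent person would ever see the case. That goes too far. Section 10.4.2 sends every SAE to the DCC/study sponsor whatever its expectedness, and the Key Roles section to which it refers was not in the text available. The DCC is an investigator, but the sponsor's independence is unshown rather than disproved.

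On capture, 10.3 requires all AEs, systemic reactions included, to be documented, and 2.7.2 has the risk discussed at consent with contact instructions. A reported case would therefore be recorded. What remains is that nobody is told to ask about these symptoms by name. The AE forms were not available and might do so.

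Finally, one might size the problem by the upper limit for no events in 10 subjects, 1 − 0.05^(1/10) = 25.9% (one-sided 95%). That limit belongs to any 10-subject study and any event. It says nothing about reporting routes, and the fix would not change it.

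**Conclusion.** The point holds as a gap in the written rules. IRB reporting of a serious or fatal distant-spread event depends on the principal investigator's own call, without a numeric reference rate in the protocol text and without an event-specific rule. If the event is graded expected, or judged not to suggest greater risk than already known, the stated rules take it to the DCC/study sponsor in 24 or 72 hours and to the IRB only if the study is halted. Separately, the risk is neither a safety endpoint nor a safety parameter, and its symptoms are not asked about by name in the visit schedule.

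The gap has no numerical size: it is zero of three event-based IRB routes for an event that is not an unanticipated problem. The conclusion assumes that the package insert, the IRB's standard protocols and the AE forms do not already close it. I would treat this as a cheap improvement well worth making, not as a flaw that blocks the study.

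**What to change.** 1. In 10.4, state that any death, life-threatening event or serious symptom of distant spread is reported to the IRB whether or not it is graded expected, on the 24-hour clock of 10.4.3. In the same edit, reconcile the clocks in 10.4 (1 business day), 10.4.1 (14 business days) and 10.4.3 (24 hours), since the new rule needs one unambiguous deadline.
2. In 4.1.3, add symptoms of distant spread as a safety endpoint. In Table 4, record it at each contact with a fixed yes/no checklist built from the 2.7.1 list: general weakness, vision, speech, swallowing, breathing, bladder control. Doing this at study visit 1 too gives each subject a baseline.

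The cost is a short protocol amendment, a six-item form taking about a minute per contact, and possibly a few extra IRB reports. Treatment and sample size do not change.

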### **10.3 Time period and frequency for event assessment and follow-up**

The occurrence of an AE or SAE may come to the attention of study personnel during study visits and interviews of a study participant presenting for medical care, or upon review by a study monitor. All AEs including local and systemic reactions not meeting the criteria for SAEs will be captured on the appropriate RF. Information to be collected includes event description, time of onset, clinician's assessment of severity, relationship to study product (assessed only by those with the training and authority to make a diagnosis), and time of resolution/stabilization of the event. All AEs occurring while on study must be documented appropriately regardless of relationship. All AEs will be followed to adequate resolution.

Any medical condition that is present at the time that the participant is screened will be considered as baseline and not reported as an AE. However, if the study participant's condition deteriorates at any time during the study, it will be recorded as an AE. UPs will be recorded in the data collection system throughout the study.

Changes in the severity of an AE will be documented to allow an assessment of the duration of the event at each level of severity to be performed. AEs characterized as intermittent require documentation of onset and duration of each episode.

The PI will record all reportable events with start dates occurring any time after informed consent is obtained until 7 (for non-serious AEs) or 30 days (for SAEs) after the last day of study participation. At each study visit, the investigator will inquire about the occurrence of AE/SAEs since the last visit. Events will be followed for outcome information until resolution or stabilization.

### **10.4 Reporting procedures**

Reporting will be performed by [name] according to HSIRB standard protocols:

#### **Immediate Report to the IRB**

An AE/SAE meeting the above definition of an unanticipated problem must be reported to the IRB immediately if **both of the following conditions are met**:

- o The event occurred at a site under the purview of the UW Health Sciences (HS) IRB or Minimal Risk (MR) IRB
- o The event is immediately life threatening or severely debilitating to other current subjects

**The IRBs expect that these reports will be rare.** SAEs that meet these conditions must be reported to the IRB Chair or IRB Director via telephone (preferred) or email as soon as possible, but no later than 1 business day after the research team becomes aware of the event. The research team will then discuss with the IRB Chair or IRB Director what action needs to be taken related to the occurrence (e.g., suspension of study enrollment, change in treatment regimen) to prevent further harm from occurring. This initial report to the IRB Chair or IRB Director must be followed with the submission of a reportable event in ARROW within 2 business days after the local research team becomes aware of the event.

#### **10.4.1 Adverse Event Reporting**

Any other AE/SAEs that meet the definition of an unanticipated problem as described above must be reported to the HS or MR IRB within 14 business days.

#### **10.4.2 Serious adverse event reporting**

The study clinician will complete a SAE Form within the following timelines:

All deaths and immediately life-threatening events, whether related or unrelated, will be recorded on the SAE Form and submitted to the DCC/study sponsor within 24 hours of site awareness. See **Section 1, Key Roles** for contact information. Other SAEs regardless of relationship, will be submitted to the DCC/study sponsor within 72 hours of site awareness.

All SAEs will be followed until satisfactory resolution or until the site investigator deems the event to be chronic or the adherence to be stable. Other supporting documentation of the event may be requested by the DCC/study sponsor and should be provided as soon as possible. The study sponsor will be responsible for notifying FDA of any unexpected fatal or life-threatening suspected adverse reaction as soon as possible but in no case later than 7 calendar days after the sponsor's initial receipt of the information.

#### **10.4.3 Unanticipated problem reporting**

The site investigator will be responsible for creating and completing a UP report form. Incidents that meet the OHRP criteria for UPs will be reported promptly on the following timeline:

- UPs that are SAEs will be reported to the IRB and to the DCC/study sponsor within 24 hours of the investigator becoming aware of the event.
- Any other UP will be reported to the IRB and to the DCC/study sponsor within 14 business days of the investigator becoming aware of the problem.
- All UPs should be reported to appropriate institutional officials (as required by an institution's written reporting procedures), the supporting agency head (or designee), and OHRP within 14 business days of the IR's receipt of the report of the problem from the investigator.

The UP report will include the following information:

- Protocol identifying information: protocol title and number, PI's name, and the IRB project number;
- A detailed description of the event, incident, experience, or outcome;
- An explanation of the basis for determining that the event, incident, experience, or outcome represents an UP;
- A description of any changes to the protocol or other corrective actions that have been taken or are proposed in response to the UP.

#### **10.5 Study Halting Rules**

This study may be temporarily suspended or prematurely terminated if there is sufficient reasonable cause. Written notification, documenting the reason for study suspension or termination, will be provided by the suspending or terminating party to the Division of PM&R and regulatory authorities. If the study is prematurely terminated or suspended, the PI will promptly inform the IRB and will provide the reason(s) for the termination or suspension.

Circumstances that may warrant termination or suspension include, but are not limited to:

- Determination of unexpected, significant, or unacceptable risk to participants
- Demonstration of efficacy that would warrant stopping
- Insufficient compliance to protocol requirements
- Data that are not sufficiently complete and/or evaluable
- Determination of futility

Study may resume once concerns about safety, protocol compliance, data quality are addressed and satisfy the sponsor, IRB and/or FDA.

#### **10.6 Safety Oversight**

The Principal Investigator will serve as the DMC. REDCap will provide the DMC and the study biostatistician the ability to efficiently collect the needed data and provide safety oversight of the protocol.

## 11 Study Monitoring, Auditing, and Inspecting

### 11.1 Medical Monitoring

The Principal Investigator will serve as the medical monitor for the study. In the design of the study, the investigators will have regular follow up with the research participants to allow close monitoring for AE/SAEs. Should AE/SAEs occur outside of clinical hours, participants will be provided at time of consent with appropriate instructions for contacting clinician for triage.

#### 11.1.1 Study Monitoring Plan

Clinical site monitoring is conducted to ensure that the rights and well-being of human subjects are protected, that the reported trial data are accurate, complete, and verifiable, and that the conduct of the trial is in compliance with the currently approved protocol/amendment(s), with GCP, and with applicable regulatory requirement(s).

- Monitoring for this study will be performed by the principal investigator
- Monitoring will be provided during all clinic visits by qualified study staff including initial assessment and 2-month follow up. He will also be responsible for monitoring participants immediately following intervention prior to a safe discharge from the clinic. The remainder of monitoring will be targeted data verification of endpoint and safety.
- PI will be provided copies of monitoring reports within 7 days of visit.
- Independent audits will not be conducted
- Investigators will perform internal quality management of study conduct, data collection, documentation and completion.

